**Table 3 Summary of Subject Assessments**

Assessments	Pre-ablation	Pre-discharge	7D (D6-8)	M1 (D23-37)	M3 (D76-104)	UNS
Clinic visit	●			● 9/10	●	●
Phone Call			● 			
Patient Informed Consent  /Demographics	●					
Medical/AF history	●					
Cardiac Medication and anti-coagulation Regimen	●	●	●	● 	●	●
CHA2DS2-Vasc Score	●					
NYHA functional Class Scale	●				●	
Pregnancy Test	● 					
Transthoracic Echo (TTE)	● 	●				
LA thrombus detection	● 					
ECG	● 	● 			● 	● 
Adverse events	●	●	●		●	●
AFL/AT/AF occurrence and repeat ablation		●	●		●	●
Endoscopy		● 				
Cerebral MRI	● 	● 		● 	● 	● 
Neurological Exam	● 	● 		● 	● 	● 
NIH Stroke Scale	● 	● 		● 	● 	● 
mRS	● 			● 	● 	● 
MoCA	● 			● 	● 	● 

1. May be substituted with a clinic visit.
2. To be completed within 60 days prior to ablation procedure
3. In all women of childbearing age and potential. To be completed within 1 week prior to ablation procedure.
4. To be performed within 30 days prior to procedure to determine the LA size and LVEF%, if the subject has undergone an imaging procedure within the last 6 months where the atrial size was assessed, the pre-procedure imaging assessment is not required.
5. To be completed the day before or the day of the study ablation procedure. Imaging modality TEE, ICE, CT or MRI.
6. To be collected if completed as standard of care.
7. To be completed within 72-hours pre-procedure.
8. To be completed within 72-hours post-procedure.
9. To be undertaken/collected if neurologic symptoms and/or new cerebral ischemic lesions identified/CVA/TIA reported in a prior evaluation.
10. To be completed only if a previous mandated test was missed, or if subject reports neurologic difficulties between scheduled follow-up visits and unscheduled assessment per investigator approval

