Primary Adverse Event	Description / Criteria
Pulmonary Vein Stenosis*	
A reduction of the diameter of a PV.
 
Severe PV stenosis (<math>\geq 70\%</math> reduction in the diameter of the PV) will be considered a primary adverse event and major complication of AF ablation.

Stroke/Cerebrovascular Accident (CVA)	
Diagnosis:
 
 
-Rapid onset of a focal or global neurological deficit with at least one of the following: change in level of consciousness, hemiplegia, hemiparesis, numbness or sensory loss affecting one side of the body, dysphasia or aphasia, hemianopia, amaurosis fugax, or other neurological signs or symptoms consistent with stroke.
 
-Duration of a focal or global neurological deficit <math>\geq 24</math> h; or <math><24</math> h, if therapeutic intervention(s) were performed (e.g. thrombolytic therapy or intracranial angioplasty); OR available neuroimaging documents a new hemorrhage or infarct; or the neurological deficit results in death.
 
-No other readily identifiable non-stroke cause for the clinical presentation (e.g., brain tumor, trauma, infection, hypoglycemia, peripheral lesion, pharmacological influences).†
 
-Confirmation of the diagnosis by at least one of the following: Neurology or neurosurgical specialist; Neuroimaging procedure (MR or CT scan or cerebral angiography); Lumbar puncture (i.e., spinal fluid analysis diagnostic of intracranial hemorrhage)
 
 
Definition:
 
Stroke: (diagnosis as above, preferably with positive neuroimaging study)
 
 
Minor—Modified Rankin score <math><2</math> at 30 and 90 days††
 
Major—Modified Rankin score <math>\geq 2</math> at 30 and 90 days
 

Transient Ischemic Attack	New focal neurological deficit with rapid symptom resolution (usually 1 to 2 h), always within 24h; neuroimaging without tissue injury.
Thromboembolism	Formation of a clot (thrombus) inside a blood vessel causing obstruction to blood flow. The thrombus can migrate (embolus) and obstruct distal vascular sites. Diagnostic tests to help detect thromboembolisms may include but are not limited to angiography (pulmonary or distal), ventilation-perfusion (V/Q) scans, venography, Doppler ultrasonography, spiral CT, and echocardiography.

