### **14.6. Analysis Sets**

The following analysis populations will be used to complete the analyses of data:

- **Safety Population:** The safety population will include all enrolled subjects who have the investigational device inserted, regardless if RF energy is delivered.
- **Effectiveness Population:** The effectiveness population will include all enrolled subjects who have had the investigational device inserted and underwent ablation with the study catheter used in conjunction with TGA mode for PVI. The subjects without any TGA mode application for PVI will be excluded from the effectiveness population.
- **Neurological Assessment Evaluable (NAE) Population:** The NAE Population will include all enrolled subjects who meet the eligibility criteria, have been treated with the study catheter and had any post-ablation neurological assessment. Assessment of incidence of new lesions or deficits requires availability of the associated pre-procedural assessment.

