5.2 Secondary Endpoints

- **Safety**
 - Incidence of Serious Adverse Device Effects (SADEs)
 - Incidence of Serious Adverse Events (SAEs) within 7 days (early-onset), >7-30 days (peri-procedural) and >30 days (late onset) of initial ablation procedure
 - Incidence of non-serious adverse events
 - Incidence of pre-and post-ablation asymptomatic and symptomatic cerebral emboli as determined by MRI evaluations
 - Incidence of new or worsening neurological deficits compared to baseline
 - Summary of NIHSS, mRS and MoCA scores at baseline and follow-up timepoints
- **Effectiveness**
 - PVI achieved with TGA mode only among all targeted veins and by subject
 - PVI achieved with combined use of TGA and Q-mode among all targeted veins and by subject
 - Ablation of acute reconnection (touch-up) among all targeted veins and by subject
 - Ablation by a non-study catheter among all targeted veins and by subject
 - Touch-up applications with TGA, Q-mode and non-study catheter applications
- **Additional analyses on procedural data, including but not limited to:**
 - Use of QDOT Micro™ catheter ablation outside the PV area
 - Use of a non-study catheter for ablation outside the PV area

- Total procedure time, mapping time, PV ablation time, total ablation time, RF application time, LA dwell time
- Total number of RF applications, % TGA applications and % Q-mode applications
- Anatomical location of touch-up applications
- Temperature, power, contact force, impedance
- Total Fluoroscopy time/dose

6 Levels of Significance

All data will be summarized by descriptive analyses. No formal statistical inference will be made. Sub-analyses will be done for subjects where TGA was the only application mode used and for subjects where applications were done through a combination of TGA and Q-mode. Where confidence intervals are used they will be two-sided 95% confidence intervals, unless stated otherwise.

7 Analysis Sets

The following analysis populations will be used to complete the analyses of data:

- **Safety Population (SP):** The safety population will include all enrolled subjects who have the investigational device inserted, regardless if RF energy is delivered. All safety analyses will be performed on the Safety Population.

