- **Effectiveness Population (EP):** The effectiveness population will include all enrolled subjects, have had the investigational device inserted and underwent ablation with the study catheter used in conjunction with TGA mode for PVI. The subjects without any TGA mode application for PVI will be excluded from the effectiveness population. All effectiveness analysis will be performed on the Effectiveness Population.
- **Neurological Assessment Evaluable (NAE) Population:** The NAE Population will include all enrolled subjects have been treated with the study catheter and have any post-ablation neurological assessment. Assessment of incidence of new lesions requires availability of pre-and post MRI. The subjects without pre-MRI but no lesion on post-MRI will be included in the NAE population. Assessment of incidence of new deficits requires availability of pre-and post-neurological evaluation. Analysis of neurological data will be performed on the NAE Population.

8 Sample Size Justification

This is a clinical feasibility study for evaluation of safety and acute performance of THERMOCOOL SMARTTOUCH® SF-5D system with TGA mode application for PVI. This clinical investigation is intended to provide preliminary estimates of safety and acute performance. Enrollment in the clinical investigation will be approximate 50 subjects,

distributed over up to 10 centers in Europe. Minimum attrition is expected for safety assessment. No more than 10% attrition is expected to assess effectiveness outcomes.

Because this study is a feasibility study, there is no statistical power calculation and no hypothesis to be tested. 50 subjects are deemed sufficient to clinically characterize safety and acute outcomes.

9 Data Monitoring Committee (DMC)

Safety review will be performed by the medical safety officer as described by Safety Management Plan.

10 Analyses to be Conducted

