10.4 Primary and Secondary Endpoint Analyses

Primary Safety

Primary safety outcome will be reported as primary adverse events (PAEs) (within 7 days of the intial mapping and ablation procedure, with exception for PV stenosis, death, tamponade and AEF). The number of events and the number and percentage of subjects experiencing primary adverse events will be reported. The primary safety endpoint will be summarized overall and by AE type, seriousness, severity, causality, anticipated or not. The Primary Safety analysis will be performed on the Safety Population.

Primary Effectiveness

Acute Procedural Success: Acute success is defined as achieving confirmation of entrance block in all targeted PVs after adenosine and/ or isoproterenol challenge. The number and percentage of subjects who have reached acute success will be summarized. Primary Effectiveness analysis will be performed on the Effectiveness Population.

Secondary Safety

The number of events and the number and percentage of subjects with SADEs, SAEs and non-SAEs during follow-up period (3 months) will be summarized overall and by AE type, seriousness, severity, causality, timing (< 7 days, 7-30 days, > 30 days), and outcome etc. The subjects with SADEs and SAEs will also be listed.

The number of events and the number and percentage of subjects with pre- and post-ablation asymptomatic and symptomatic cerebral emboli as determined by MRI evalutaions will be summarized. The incidence of new or worsening neurological deficits compared to baseline will be summarized and listed. NIHSS, mRS and MoCA scores at baseline and follow-up timepoints will be summarized and listed as well. The NAE endpoints will be analyzed in the NAE population.

Secondary Effectiveness

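### SAP 7 makes the new-deficit endpoint depend on a pair of neurological evaluations, so a confirmed stroke or TIA in a subject without the pair drops out of it, and the SAP does not say whether a resolved TIA counts

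*SAP*

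**What the plan says.** The endpoint in SAP 5.2 is "Incidence of new or worsening neurological deficits compared to baseline". SAP 10.4 adds only this: "The incidence of new or worsening neurological deficits compared to baseline will be summarized and listed". Neither sentence names the instrument, the size of change or the timepoint, and neither says whether a clinically diagnosed stroke or TIA is a deficit for this purpose.

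SAP 7 sets the condition: "Assessment of incidence of new deficits requires availability of pre-and post-neurological evaluation". The Neurological Assessment Evaluable (NAE) population consists of enrolled subjects "treated with the study catheter and have any post-ablation neurological assessment", and SAP 10.4 confirms that "The NAE endpoints will be analyzed in the NAE population". Protocol 14.6 has a similar condition: "Assessment of incidence of new lesions or deficits requires availability of the associated pre-procedural assessment". SAP 10.6 rules out imputation, and SAP 10.1 bases percentages on subjects without missing data.

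Stroke and TIA are also primary adverse events (PAEs) within 7 days of the procedure (SAP 5.1). They are analysed in the Safety Population, which needs only insertion of the device (SAP 7, 10.4). Protocol Table 4 describes a TIA as "New focal neurological deficit with rapid symptom resolution (usually 1 to 2 h), always within 24h". The one post-procedure neurological examination scheduled for every subject is "To be completed within 72-hours post-procedure" (Protocol Table 3, footnote 8).

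**The concern.** The subjects most likely to lack an evaluation may include those with the worst outcomes, for example a subject who dies before being examined. A rule that requires both evaluations removes such a subject from the numerator and the denominator. The result can then only look better.

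SAP 7 relaxes pairing in one place, for MRI: a subject without a pre-procedure scan is kept if the post-procedure scan shows no lesion. That is logical as far as it goes, but it helps only favourable results. No matching rule keeps a subject whose pair is incomplete but whose stroke is confirmed. Exclusion criterion 32 already bars an unresolved pre-existing deficit, so a stroke after the procedure can be recognised as new without a baseline score.

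The report could therefore show a stroke or TIA in the primary safety table and no new deficits in the secondary table, with nothing in the plan to explain the difference.

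**Working it through.** **Inputs.** The Safety Population is taken as 50: Protocol 4.3.2 aims for 50 evaluable subjects, and Protocol 4.4 defines evaluable as having the catheter inserted. The documents give no expected rate of stroke, TIA or missing pairs, so the event counts below are assumptions. There is no stated figure to reproduce: SAP 8 says there is no power calculation, and no rate is given for this endpoint.

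**Step 1: follow each kind of subject, with the event inside 7 days.**

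| Subject | PAE table (Safety Population) | New-deficit result (SAP 7) |
|---|---|---|
| Stroke, both evaluations done | Counted | Evaluable; counted if the examination shows it |
| Stroke or TIA, baseline evaluation missed | Counted | Not assessable; out of numerator and denominator |
| Stroke, death or exit before any post-ablation assessment | Counted | Outside the NAE population |
| Stroke or TIA, catheter inserted but no ablation | Counted | Outside the NAE population, reading treated as ablated |
| TIA resolved, both evaluations done | Counted | In the denominator; numerator not defined |

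Rows 2 to 4 follow from the stated rule. Row 5 is a missing definition.

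**Step 2: timing of the TIA case.** A TIA resolves within 24 hours. The common examination may take place up to 72 hours after the procedure and is done before discharge (Protocol 8.2.4). The day-7 contact may be a telephone call. A TIA that clears before the examination, or occurs after it, can leave every paired examination clean. An examination-only reading would then score no deficit.

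**Step 3: size.** Exact (Clopper-Pearson) two-sided 95% limits. The SAP does not prescribe this method. For 0/n the upper limit is 1 − 0.025^(1/n). For 1/50 the lower limit is 1 − 0.975^(1/50), and the upper limit p solves (1 − p)^50 + 50p(1 − p)^49 = 0.025.

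- One stroke, counted in all subjects: 1/50 = 2.0% (0.05% to 10.65%).
- The same stroke in the only unpaired subject: 0/49 = 0%, upper limit 1 − 0.025^(1/49) = 7.25%.
- Five unpaired subjects, one of them with the stroke: 0/45 = 0%, upper limit 1 − 0.025^(1/45) = 7.87%.
- One resolved TIA in a paired subject: 1/50 = 2.0% or 0/50 (upper limit 1 − 0.025^(1/50) = 7.11%), depending on the definition chosen.

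**Step 4: how often this could arise.** The chance of at least one event in 50 subjects is 1 − (1 − p)^50. At assumed rates of 0.5%, 1% and 2% this is 22%, 39% and 64%. These figures are ceilings on the chance of a mismatch at those rates, because the event must also fall in a subject without a pair or be a TIA left uncounted.

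**The case against.** The strongest reply is that the quoted sentence says whose data can be assessed and does not define a deficit. That is correct. A reader might infer that the SAP scores every resolved TIA as no deficit, but the text does not go that far. A subject with a resolved TIA and both evaluations is evaluable, and Table 4 itself calls a TIA a new focal deficit. For that subject the supportable finding is an open definition.

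A reader might also infer that everything hangs on one 72-hour examination. The documents do not support that either. NAE entry has no time limit on the post-ablation assessment. Missed tests can be made up at an unscheduled visit (Table 3, footnote 10). A deficit, CVA or TIA found at a prior evaluation triggers a month-1 examination (Protocol 8.3), and stroke grading uses the mRS at 30 and 90 days. The baseline evaluation is mandatory (Protocol 8.2.1). A surviving stroke subject would ordinarily have a post-ablation assessment. What stands is the remainder: a later visit cannot recreate a missed pre-procedure baseline, and it cannot examine a subject who has died or left.

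Nor is a safety signal lost. PAEs are SAEs (Protocol 9.1.3), and SAP 10.4 summarises SAEs over 3 months and lists the subjects. A stroke or TIA after day 7 is not a PAE, so for later events the comparison is with the SAE tables only.

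Finally, a paired-examination endpoint beside an adverse-event endpoint is a legitimate design. That is so if it is labelled as such, which this one is not.

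**Conclusion.** The point holds in a limited form. By stated rule, a confirmed stroke or TIA in a subject without both evaluations, or who was never ablated, is excluded from the new-deficit endpoint. For a resolved TIA in a subject with both evaluations, the SAP leaves the decision open, to be made once the data are known.

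The consequence is a possibly understated secondary rate and tables that may contradict each other. In about 50 subjects one event is worth 2.0 percentage points, so a single case decides between 2.0% and zero. This rests on assumed counts: the documents give no rate of missing pairs, so a downward bias is possible and its size is unknown. The endpoint is descriptive and secondary, and no hypothesis depends on it. The change should be made because it is cheap and removes a choice after the data are known.

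**What to change.** In SAP 7 and 10.4:

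1. Count a subject as having a new or worsening deficit if the paired examination or NIHSS shows one, or if a confirmed stroke, TIA or other neurological-deficit adverse event with onset at or after the index procedure is recorded, whether or not a pair exists. State which instrument, change and timepoint define the paired component.
2. Report this rate over the whole Safety Population. The denominator must not depend on outcome. If unpaired subjects were added only when they had an event, the example with five unpaired subjects would give 1/46 = 2.2% in place of 1/50 = 2.0%.
3. Show the paired-examination-only rate in the NAE population as a second row, and state the number of subjects without a pair.
4. Align SAP 7, which assigns all safety analyses to the Safety Population and neurological data to the NAE population.

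The cost is SAP wording. Adverse events are already collected from consent to study end (Protocol 9.4.1). Protocol 14.8.4.3 places the neurological endpoints in the NAE population, so the SAP should state the added Safety Population row as a departure. The reported rate may be slightly less favourable, and event-free subjects without a pair will be classified by adverse event reporting alone.

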10.1 General Conventions

All data will be summarized by descriptive analyses. No formal statistical inference will be made.

Standard descriptive summaries for continuous data include the number of observations with data, mean, standard deviation, median, minimum, and maximum values. For categorical data, the count and percent will be provided. Percentages will be based on the number of subjects without missing data.

10.2 Disposition of Study Subjects

The subject accountability and disposition will be summarized in tables for all enrolled subjects and listings will be provided.

10.3 Demographic and Baseline Characteristics

Age at consent will be summarized with sample size, mean, standard deviation, median, quartiles, and min and max. Gender will be summarized with counts and percentages. Baseline Medical History information and baseline medical scores will be summarized with sample size, mean, standard deviation, median, quartiles, minimum, and maximum for continuous variables and with counts and percentages for categorical variables.

Baseline assessments includes:

- Demographics (age, gender).
- Medical history: arrhythmia, heart disease, thromboembolic events
- AF history
- Medication history
- AAD medication
- CHA2DS2 VASc Score

- Transthoracic Echo (TTE)
- Electrocardiogram (12-Lead ECG)
- Adverse Events
- Cerebral MRI, Neurological Exam and Neurological Evaluation using the Montreal Cognitive Assessment (MoCA), NIH Stroke Scale (NIHSS) and Modified Rankin Scale (mRS)

10.4 Primary and Secondary Endpoint Analyses

Primary Safety

Primary safety outcome will be reported as primary adverse events (PAEs) (within 7 days of the intial mapping and ablation procedure, with exception for PV stenosis, death, tamponade and AEF). The number of events and the number and percentage of subjects experiencing primary adverse events will be reported. The primary safety endpoint will be summarized overall and by AE type, seriousness, severity, causality, anticipated or not. The Primary Safety analysis will be performed on the Safety Population.

Primary Effectiveness

Acute Procedural Success: Acute success is defined as achieving confirmation of entrance block in all targeted PVs after adenosine and/ or isoproterenol challenge. The number and percentage of subjects who have reached acute success will be summarized. Primary Effectiveness analysis will be performed on the Effectiveness Population.

Secondary Safety

The number of events and the number and percentage of subjects with SADEs, SAEs and non-SAEs during follow-up period (3 months) will be summarized overall and by AE type, seriousness, severity, causality, timing (< 7 days, 7-30 days, > 30 days), and outcome etc. The subjects with SADEs and SAEs will also be listed.

The number of events and the number and percentage of subjects with pre- and post-ablation asymptomatic and symptomatic cerebral emboli as determined by MRI evalutaions will be summarized. The incidence of new or worsening neurological deficits compared to baseline will be summarized and listed. NIHSS, mRS and MoCA scores at baseline and follow-up timepoints will be summarized and listed as well. The NAE endpoints will be analyzed in the NAE population.

Secondary Effectiveness

The number of PV isolation achieved among all targeted veins and the number and percentage of subjects with PVI achieved with TGA mode only will be summarized and listed. The number of PV isolation achieved among all targeted veins and the number and percentage of subjects with PVI achieved with combined use of TGA and Q-mode will be summarized and listed. The number of PV with acute reconnection (touch-up) among all targeted veins and the number and percentage of subjects with touch-up ablations will be summarized and listed. Touch-up applications with TGA, Q-mode and non-study catheter will be summarized by PVs and subjects. PV ablations by a non-study catheter among all targeted veins and by subject will be summarized and listed. These analyses will be performed in the effectiveness population.

Additional Analyses on Procedural Data

Procedural data will be summarized and listed. For continuous variables, number of subjects with non-missing data, mean, standard deviation, median, 25% percentile, 75% percentile, minimum, and maximum will be reported. For categorical variables, the frequency and percentage will be presented for each category. Procedural data will be summarized in the effectiveness population.

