### 3.2. Study Endpoints

#### 3.2.1. Primary Endpoint(s)

##### Acute Safety

The primary safety endpoint is the incidence of Primary Adverse Events (PAEs) (within seven (7) days of the initial mapping and ablation procedure). Primary Adverse Events are one of the following adverse events listed below. (refer to section 9.1.3 for a complete list and description/criteria).

Atrio-Esophageal Fistula (AEF)*	Phrenic Nerve Paralysis (PNP)
Cardiac Tamponade/perforation	Pulmonary Vein Stenosis*
Death*	Stroke/CVA
Major Vascular Access Complication/Bleeding	Thromboembolism
Myocardial Infarction	TIA

\* Device or procedure related death, pulmonary vein stenosis and atrio-esophageal fistula, that occur greater than one week (7 days) post-procedure are considered and analyzed as primary AEs.

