### 9.1.3. Primary Adverse Event (PAE)

A Primary AEs is an event listed in Table 4 which occurs within the first week (7 days) following an ablation procedure. Primary AEs are considered SAEs.

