**Table 4 Primary Adverse Events**

Primary Adverse Event	Description / Criteria
Atrio-Esophageal Fistula*	Defined as a connection between the atrium and the lumen of the esophagus. Evidence supporting this diagnosis includes documentation of esophagus erosion combined with evidence of a fistulous connection to the atrium such as air emboli, an embolic event, or direct observation at the time of surgical repair. A CT or MRI scan is the most common method of documentation of an atrio-esophageal fistula.
Cardiac Tamponade**/Perforation	
The development of a significant pericardial effusion during or within 30 days of undergoing the index AF ablation procedure. A significant pericardial effusion is one that results in hemodynamic compromise, requires elective or urgent pericardiocentesis, or results in a 1cm or more pericardial effusion as documented by echocardiography
 
Cardiac tamponade/perforation should also be classified as:
 
Early – diagnosed prior to discharge
 
Late – following initial discharge from the hospital

Death*	Subject death directly related to the device or procedure and occurs at any time during or after the procedure.
Major Vascular Access Complication /Bleeding	
Major Bleeding:
 
Requires and/or treated with transfusion or results in a 20% or greater fall in hematocrit.
 
Major Vascular Access Complication:
 
Defined as a hematoma, an AV fistula or a pseudoaneurysm which requires intervention such as surgical repair or transfusion, prolongs the hospital stay, or requires hospital admission.

Myocardial Infarction	
Presence of any one of the following criteria:
 

– Detection of ECG changes indicative of new ischemia (new ST-T changes or new left bundle branch block [LBBB]) that persist for more than 1 hour

– Development of new pathological Q waves on ECG

– Imaging evidence of new loss of viable myocardium or new regional wall motion abnormality

Phrenic Nerve Paralysis	Absent phrenic nerve function as assessed by a sniff test, and associated with symptoms of dyspnea and orthopnea (diagnosed by chest x-ray). A phrenic nerve paralysis is considered to be permanent when it is documented to be present 12 months or longer following ablation. Under this protocol, diaphragmatic paralysis/phrenic nerve palsy will be considered a Primary AE if specified symptoms have not improved at the 3-month final visit

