\* Device or procedure related death, atrio-esophageal fistula and pulmonary vein stenosis that occur greater than one week (7 days) post-procedure shall be deemed Primary AE.

\*\* Hemodynamic compromise or instability is defined as Systolic blood pressure  $< 80$  mmHg

† Patients with non-focal global encephalopathy will not be reported as a stroke without unequivocal evidence based upon neuroimaging studies.

†† mRS assessments should be made by qualified individuals according to a certification process. If there is discordance between the 30 and 90 day mRS, a final determination of major versus minor stroke will be adjudicated by an independent physician/committee.

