### 14.4. Primary and Secondary Endpoints, and Associated Hypotheses

#### 14.4.1. Primary Endpoints and Associated Hypotheses

The primary safety endpoint is acute safety defined as the Primary Adverse Events (PAEs) within the first 7 days. PAEs include the following AEs:

Atrio-Esophageal Fistula*	Phrenic Nerve Paralysis
Cardiac Tamponade/perforation	Pulmonary Vein Stenosis*
Death*	Stroke/CVA
Major Vascular Access Complication/Bleeding	Thromboembolism
Myocardial Infarction	TIA

\*Device or procedure related death, pulmonary vein stenosis and atrio-esophageal fistula that occur greater than one week (7 days) post-procedure are considered and analyzed as primary AEs.

The primary effectiveness endpoint is acute procedural success defined as achieving confirmation of entrance block in all targeted PVs after adenosine and/ or isoproterenol challenge. The use of non-study catheter for PVI will be considered as an effectiveness failure.

No formal statistical hypotheses will be formulated and performed for the primary endpoints.

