5.1 Primary Endpoint(s) and Associated Hypotheses

Acute Safety

The primary safety endpoint is the incidence of Primary Adverse Events (PAEs) (within seven (7) days of the initial mapping and ablation procedure). PAEs include the following AEs:

Atrio-Esophageal Fistula*	Phrenic Nerve Paralysis
---------------------------	-------------------------

Cardiac Tamponade/perforation	Pulmonary Vein Stenosis*
Death*	Stroke/CVA
Major Vascular Access Complication/Bleeding	Thromboembolism
Myocardial Infarction	TIA

**Device or procedure related death, pulmonary vein stenosis and atrio-esophageal fistula that occur greater than one week (7 days) post-procedure are considered and analyzed as primary AEs.*

Acute Effectiveness

Acute Procedural Success defined as confirmation of entrance block in all targeted PVs after adenosine and/or isoproterenol challenge. The use of a non-study catheter for PVI will be considered an effectiveness failure.

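### SAP 5.1 and SAP 10.4 apply different late-event rules to the primary safety endpoint: 10.4 exempts tamponade from the 7-day window and drops the relatedness condition on death

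*SAP*

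**What the plan says.** SAP 5.1 lists ten PAE types and marks three with an asterisk. The note reads: "Device or procedure related death, pulmonary vein stenosis and atrio-esophageal fistula that occur greater than one week (7 days) post-procedure are considered" primary events. Tamponade/perforation is in the list without an asterisk. SAP 10.4 keeps the 7-day window but writes "with exception for PV stenosis, death, tamponade and AEF", with no relatedness condition on death and no reference to an outer limit.

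The protocol points both ways.

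- Table 4 describes tamponade/perforation as "The development of a significant pericardial effusion during or within 30 days of undergoing the index AF ablation procedure". Section 3.2.1 sends the reader to that material: "refer to section 9.1.3 for a complete list and description/criteria".
- The footnote to the same table names three late events only: "Device or procedure related death, atrio-esophageal fistula and pulmonary vein stenosis that occur greater than one week (7 days) post-procedure shall be deemed Primary AE". Section 14.4.1 says "The primary safety endpoint is acute safety defined as the Primary Adverse Events (PAEs) within the first 7 days" and repeats the three-event footnote, as do 3.2.1 and the Protocol Summary.
- The sentence that introduces Table 4 in section 9.1.3 gives 7 days with no exception at all.
- Section 14.8.4.1, the protocol's analysis paragraph, exempts only PV stenosis and AEF.

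On timing categories, SAP 5.2 puts day 7 in the first period (up to and including 7 days, then after 7 to 30, then after 30). The secondary safety paragraph of SAP 10.4 puts day 7 in the second (under 7, 7 to 30, over 30).

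**The concern.** SAP 5.1 and 10.4 are both current text of one plan, and a programmer who follows one will not always get the result of the other. The endpoint is the primary safety outcome of a single-arm, unblinded feasibility study, and its whole output is a count of events and a count and percentage of subjects. If a tamponade appears in the second, third or fourth week, someone must choose a rule, and by then the event will be known. One pre-stated window removes that choice.

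**Working it through.** **Step 1: line up the lists.** Events that each text allows to count after day 7:

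| Text | Death | PV stenosis | AEF | Tamponade/perforation |
|---|---|---|---|---|
| SAP 5.1 | if related | yes | yes | no |
| SAP 10.4 | yes, no condition stated | yes | yes | yes, no limit stated |
| Protocol 9.1.3, introductory sentence | no | no | no | no |
| Protocol Table 4, event criterion | if related, at any time | no time stated | no time stated | to day 30 |
| Protocol Table 4 footnote | if related | yes | yes | no |
| Protocol 3.2.1 and 14.4.1 footnotes | if related | yes | yes | no |
| Protocol 14.8.4.1 | no | yes | yes | no |

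**Step 2: classify one case.** Take a first tamponade or perforation diagnosed on days 8 to 30. Under SAP 5.1 it is outside the window and not among the exceptions, so it is not a PAE. Under SAP 10.4 it is exempt from the window and meets the Table 4 criterion, so it is a PAE.

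**Step 3: size.** The plan gives no figure to reproduce, because it disclaims a power calculation and a hypothesis. The input is N = 50 (Protocol 14.7; about 50 in SAP section 8).

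- Event count: +1 for each such event, whether or not the subject already has a PAE.
- Subject rate: changes by 1/N for each such subject who has no other PAE. 1/50 = 2.0 percentage points.
- The SAP does not commit to an exact N. For an assumed range of 45 to 55, the step is 1/45 = 2.2 points down to 1/55 = 1.8 points.

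SAP 10.4 specifies no interval for this endpoint. For scale only, exact (Clopper-Pearson) two-sided 95% intervals at N = 50 are:

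| Subjects with a PAE | Rate | 95% interval |
|---|---|---|
| 0 | 0% | 0% to 7.11% |
| 1 | 2.0% | 0.05% to 10.65% |
| 2 | 4.0% | 0.49% to 13.71% |

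**Step 4: how often.** Protocol 1.4.1 cites tamponade in 4/161 (2.48%) and 2/159 (1.3%) subjects in two earlier catheter studies, but does not say when those events occurred. The chance of a day 8 to 30 case cannot be derived from the documents, so I give none.

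**Step 5: death.** Read literally, SAP 10.4 would also count an unrelated death after day 7, which 5.1 would not. Table 4 limits the death PAE to deaths related to the device or procedure, so the literal reading arises only if Table 4 is left out of account.

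**Step 6: timing bins.** An adverse event on day 7 falls in the first bin under SAP 5.2 and in the second under SAP 10.4. Events on other days are unaffected.

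**The case against.** The best defence is that a working rule can already be found. Table 4 holds the detailed criteria, section 3.2.1 refers to it, and it gives tamponade 30 days. SAP 10.4 is the analysis section and names tamponade expressly. The study has no hypothesis or success threshold, no echocardiogram is scheduled after discharge (Table 3), and a late tamponade would appear in the adverse event tables by type and timing under either rule. In section 14.8.4.1, the omission of late related death is largely answered by the footnote in 14.4.1.

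Most of that stands. It shows that the documents lean towards 30 days and that the consequence is small. It does not show that the rule is settled, because SAP 5.1 and the footnote to Table 4 itself leave tamponade out of the late events, and no text says which prevails.

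A reader might also infer three stronger things that the documents do not support.

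- *That the choice of SAP section decides whether a late effusion is serious.* Table 4 does count an effusion that "results in a 1cm or more pericardial effusion as documented by echocardiography" even without compromise or drainage, and section 9.1.3 says "Primary AEs are considered SAEs". But seriousness is defined in Protocol 9.1.2 and 9.1.3 and determined by the sponsor under 9.4.1, and SAP 10.4 treats it as a separate attribute of the event. What remains is a question inside the protocol: which window the rule in 9.1.3 uses.
- *That late tamponade has no outer limit.* Table 4 gives one. What the SAP lacks is a cross-reference.
- *That the two SAP sections agree in every case but a late tamponade in a subject with no other PAE.* The condition on death differs as well, and the event count can differ when the subject rate does not.

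**Conclusion.** The inconsistency is real and should be corrected before analysis. SAP 5.1 and 10.4 give different primary safety results when a first tamponade or perforation falls on days 8 to 30: one more event under 10.4 and, if the subject has no other PAE, one more subject, worth 2.0 points at N = 50. They would also differ on an unrelated late death if 10.4 were read literally. If neither occurs, the results are the same. The day-7 mismatch in the timing bins is a separate, smaller error.

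This rests on the current wording and on N close to 50. It does not rest on any assumed rate of late tamponade. That the rule might be picked after the event is known is a possibility left open by the wording, not something the documents show is intended.

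**What to change.** In the SAP, before any analysis:

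- Reconcile 5.1 and 10.4 to one window per event type by cross-reference to Protocol Table 4. Its 30-day tamponade criterion is the reading consistent with 10.4.
- Restore to 10.4 the condition that a late death must be related to the device or procedure.
- Change the 10.4 timing bins to those of 5.2.

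In the protocol, at the next amendment:

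- Bring the opening of 9.1.3, the Table 4 footnote, 14.4.1 and 14.8.4.1 to the same window, with late related death included in 14.8.4.1. The matching footnotes in the Protocol Summary and 3.2.1 should follow.
- State that the 9.1.3 rule making primary events serious uses that window.

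The cost is wording. Section 11 of the protocol allows abbreviated approval for administrative changes, if this qualifies as one. No visits, data or subjects are added. With the 30-day window the reported PAE rate may be slightly less favourable than with 7 days.
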